8. ETHICAL AND REGULATORY REQUIREMENTS

8.1 Ethical conduct of the study

The study will be performed in accordance with ethical principles that have their origin in the Declaration of Helsinki and are consistent with ICH/Good Clinical Practice, applicable regulatory requirements and the AstraZeneca policy on Bioethics and Human Biological Samples.

The applicable regulatory requirements in Japan are ‘Good Clinical Practice for Trials on Drugs (MHLW Ordinance No. 28, 27 March 1997, partially revised by MHLW Ordinance and their related notifications.

8.2 Subject data protection

The Master Informed Consent Form will explain that: Study data will be stored in a computer database, maintaining confidentiality in accordance with national data legislation. Subject data will be maintained confidentially in accordance with national data legislation. For data verification purposes, authorised representatives of AstraZeneca, a regulatory authority or an Ethics Committee may require direct access to parts of the hospital or practice records relevant to the study, including subjects’ medical history. All data computer processed by AstraZeneca will be identified by study code and enrolment code (E-code).

8.3 Ethics and regulatory review

An Ethics Committee should approve the final study protocol, including the final version of the Informed Consent Form and any other written information and/or materials to be provided to the subjects. The Head of the study site will ensure the distribution of these documents to the applicable Ethics Committee, and to the study site staff.

The head of the study site must submit a notification of direction/determination as well as a copy of the IRB written approval to AstraZeneca before enrolment of any subject should into the study.

The Ethics Committee should approve all advertising used to recruit subjects for the study.

AstraZeneca should approve any modifications to the Informed Consent Form that are needed to meet local requirements.

The protocol should be re-approved by the IRB annually.

Before enrolment of any subject into the study, the final study protocol, including the final version of the Informed Consent Form, to be approved by the national regulatory authority or a notification to the national regulatory authority is to be done, according to local regulations.

AstraZeneca will handle the distribution of any of these documents to the national regulatory authorities.

AstraZeneca will provide Regulatory Authorities, Ethics Committees and Principal Investigators with safety updates/reports according to local requirements, including SUSARs (Suspected Unexpected Serious Adverse Reactions), where relevant.

8.4 Informed consent

The Principal Investigator(s) at each centre will:

- Ensure each subject is given full and adequate oral and written information about the nature, purpose, possible risk and benefit of the study
- Ensure each subject is notified that they are free to discontinue from the study at any time
- Ensure that each subject is given the opportunity to ask questions and allowed time to consider the information provided
- Ensure each subject provides signed and dated informed consent before conducting any procedure specifically for the study
- Ensure the original, signed Informed Consent Form(s) is/are stored in the Investigator's Study File
- Ensure a copy of the signed Informed Consent Form is given to the subject
- Ensure that any incentives for subjects who participate in the study as well as any provisions for subjects harmed as a consequence of study participation are described in the informed consent form that is approved by an Ethics Committee.

If any new information on the study medication becomes available which may influence the decision of the subject to continue the study, the investigator(s) should inform the subject of such information immediately, record this in a written form, and confirm with the subject if he or she wishes to continue the participation in the study. In addition, if the investigator(s) deem it necessary to revise the Informed Consent Form, they should revise it immediately (Refer to Section 8.5). The investigator(s) should explain the updated Informed Consent Form to the subjects even if the subjects have already been informed of the new information verbally. Written informed consent to continue participation in the study should be provided separately.

8.5 Changes to the protocol and informed consent form

Study procedures will not be changed without the mutual agreement of the Principal Investigator and AstraZeneca. If it is necessary for the study protocol to be amended, the amendment should be submitted to the Head of the Study Site and be approved by its IRB. If applicable, AstraZeneca should submit a notification to the regulatory authority before it is implemented. If a protocol amendment requires a change to a particular centre's Informed Consent Form, then AstraZeneca and the centre's IRB should be notified. Approval of the revised Informed Consent Form by AstraZeneca and by the IRB is required before the revised form is used. If an administrative change is required, such a change should be notified to or approved by each IRB according to local requirements.

8.6 Audits and inspections

Authorised representatives of AstraZeneca, a regulatory authority, or an Ethics Committee may perform audits or inspections at the centre, including source data verification. The purpose of an audit or inspection is to systematically and independently examine all study-related activities and documents, to determine whether these activities were conducted, and data were recorded, analysed, and accurately reported according to the protocol, Good Clinical Practice (GCP), guidelines of the International Conference on Harmonisation (ICH), and any applicable regulatory requirements. The investigator will contact AstraZeneca immediately if contacted by a regulatory agency about an inspection at the centre.

All study data may undergo a reliability review and onsite-GCP inspection by the regulatory authorities.

9. STUDY MANAGEMENT BY ASTRAZENECA

9.1 Pre-study activities

Before the first subject is entered into the study, it is necessary for a representative of AstraZeneca to visit the investigational study site to:

- Determine the adequacy of the facilities
- Determine availability of appropriate subjects for the study
- Discuss with the investigator(s) (and other personnel involved with the study) their responsibilities with regard to protocol adherence, and the responsibilities of AstraZeneca or its representatives. This will be documented in a Clinical Study Agreement between AstraZeneca and the investigator.

9.2 Training of study site personnel

Before the first subject is entered into the study, an AstraZeneca representative will review and discuss the requirements of the Clinical Study Protocol and related documents with the

investigational staff and also train them in any study specific procedures and the WBDC system(s) utilised.

The Principal Investigator will ensure that appropriate training relevant to the study is given to all of these staff, and that any new information relevant to the performance of this study is forwarded to the staff involved.

The Principal Investigator will maintain a record of all individuals involved in the study (medical, nursing and other staff).

9.3 Monitoring of the study

During the study, an AstraZeneca representative will have regular contacts with the study site, including visits to:

- Provide information and support to the investigator(s)
- Confirm that facilities remain acceptable
- Confirm that the investigational team is adhering to the protocol, that data are being accurately and timely recorded in the CRFs, that biological samples are handled in accordance with the Laboratory Manual and that investigational product accountability checks are being performed
- Perform source data verification (a comparison of the data in the CRFs with the subject's medical records at the hospital or practice, and other records relevant to the study) including verification of informed consent of participating subjects. This will require direct access to all original records for each subject (eg, clinic charts)
- Ensure withdrawal of informed consent to the use of the subject's biological samples is reported and biological samples are identified and disposed of/destroyed accordingly, and the action is documented, and reported to the subject.

The AstraZeneca representative will be available between visits if the investigator(s) or other staff at the centre needs information and advice about the study conduct.

9.3.1 Source data

Source data are any data generated as a result of the subject's inclusion in the study (including run-in and/or follow up related to the study) and includes all related medical examinations and other records.

Original data recorded on the CRFs and regarded as source data are as follows.

- Reason for therapy or medication
- Any Comments on CRF

- Evaluation for inclusion/exclusion criteria on CRIT
- Adverse Event (Yes/No, Maximum intensity, Serious, Treatment required, Outcome, Causality)
- Description of AE on Serious Adverse Event form
- Main reason for premature discontinuation

9.3.2 Direct access to source data in Japan

The Head of the institution and the Principal Investigator/sub-investigator will cooperate for monitoring and audit by AstraZeneca, and accept inspection by the IRB or regulatory authorities. All study documents such as raw data will be open for direct access to source data at the request of the monitor and the auditor of AstraZeneca, the IRB, or regulatory authorities.

The monitor(s) will verify data from the CRFs against source data before collecting the CRFs to ensure accuracy and completeness of documentation, and assure that the Principal Investigator/sub-investigator has submitted the CRFs to AstraZeneca. If the investigator wishes to amend the collected CRFs, the monitor will ensure that the Principal Investigator/sub-investigator has documented the amendment in writing (signed and dated) and provided this to AstraZeneca.

9.4 Study agreements

The Principal Investigator at each/the centre must comply with all the terms, conditions, and obligations of the Clinical Study Agreement, or equivalent, for this study. In the event of any inconsistency between this Clinical Study Protocol and the Clinical Study Agreement, the terms of Clinical Study Protocol shall prevail with respect to the conduct of the study and the treatment of subjects and in all other respects, not relating to study conduct or treatment of subjects, the terms of the Clinical Study Agreement shall prevail.

Agreements between AstraZeneca and the Principal Investigator must be in place before any study-related procedures can take place, or subjects are enrolled.

9.4.1 Archiving of study documents

- (i) **Study files.** AstraZeneca will provide the Principal Investigator with a file in which to organise and retain all study-related documents. All study documents (including letters from AstraZeneca) should be retained in this file by the Principal Investigator. The monitor will regularly check the file to ensure that all relevant documents are retained. The contents of the file may be audited/inspected by AstraZeneca's auditor, regulatory authorities, or IRB.
- (ii) **Period of record retention.** The study site (and the Principal Investigator) will retain the essential documents specified in the ICH GCP (eg, source document such as medical records, contract, signed consent form). Essential documents should be

retained at the study site for at least 15 years following completion of the study, or per regulatory obligations if longer, and thereafter destroyed only after agreement with AstraZeneca. However this is not always applied to those that are not preservable such as blood samples. In the event of any inconsistency between the above-mentioned contents and the contract with the study site, the contract shall prevail. These documents should be retained for a longer period however if needed by AstraZeneca, and the specific period and method of retention will be separately discussed between the study site and AstraZeneca. AstraZeneca should notify the head of the study site in writing when the study related records are no longer needed. The records should be managed by a responsible person appointed by the head of the study site.

9.4.2 Deviation from the clinical study protocol in Japan

Investigator(s) must not deviate from or make any changes to the protocol without documented agreement between the principal investigator and AstraZeneca or the IRB approval based on its deliberations. However, this shall not apply to cases where the deviation or change is necessary to avoid an immediate hazard to the patients or for other compelling medical reasons, or where the changes involve only logistical or administrative aspects of the clinical trial (e.g. changes to the organisation/structure of the sponsor, the name/department name of the medical institution, the address or phone number of the medical institution or the sponsor, the job title of the investigator, and monitors). In such case, the principal investigator must notify details of the deviation or change, the reason, and a proposed revision in the protocol if required, to AstraZeneca and the head of the study site and IRB via the head of the study site as soon as possible, in order to obtain their approval. A certificate of approval by the head of the study site as well as AstraZeneca should be obtained via the head of the study site.

The investigator(s) should document any deviation from the protocol regardless of their reasons. Only when the protocol was not followed in order to avoid an immediate hazard to the patients or for other medically compelling reason, the investigator should prepare and submit the records explaining the reasons thereof to the sponsor, and retain a copy of the records.

9.5 Study timetable and end of study

The end of the study is defined as ‘the last visit of the last subject undergoing the study’.

The study may be terminated at individual centres if the study procedures are not being performed according to GCP, or if recruitment is slow. AstraZeneca may also terminate the entire study prematurely if concerns for safety arise within this study or in any other study with dapagliflozin.

Planned duration of the study:

Study period: January 2010 – April 2010

Registration period: January 2010 – April 2010

Discontinuation or suspension of the whole study programme

If AstraZeneca decides to prematurely terminate or suspend the study, the Principal Investigator, the head of the institution, and regulatory authorities should receive written notification of the reasons for the premature termination or suspension.

The Principal Investigator/sub-investigator will immediately notify the decision to the subjects, give appropriate medical treatment; take necessary measures, and record treatment or measures provided on the source documents.

Completion of the study

Upon terminating the study, the Principal Investigator will report in writing the completion of the study as well as the summary of the results to the head of the study site in accordance with the institution's rules. The head of the study site, who is informed of the termination by the investigator, will provide a written notification of the results to the IRB and AstraZeneca.

10. DATA MANAGEMENT BY ASTRAZENECA DATA MANAGEMENT CENTRE

Data management will be performed by AstraZeneca Data Management Centre staff.

The data collected through third party sources will be obtained and reconciled against study data.

Adverse events and medical/surgical history will be classified according to the terminology of the latest version the Medical Dictionary for Regulatory Activities (MedDRA). Medications will be classified according to the Bristol-Myers Squibb Drug Dictionary. All coding will be performed by the Medical Coding Team at Bristol-Myers Squibb.

Data queries will be raised for inconsistent, impossible or missing data. All entries to the study database will be available in an audit trail.

The data will be validated as defined in the Data Management Plan. Quality control procedures will be applied to each stage of data handling to ensure that all data are reliable and have been processed correctly.

When all data have been coded, validated, signed and locked, clean file will be declared. Any treatment revealing data may thereafter be added and the final database will be locked.

Data associated with biological samples will be transferred to laboratories internal or external to AstraZeneca.

Management of external data

Data Management determines the format of the data to be received from external vendors and coordinates the flow of data to an external environment or clinical database (if applicable).

Data Management will ensure that the data collection tool will be tested / validated as needed. External data reconciliation will be done with the clinical database as applicable.

11. EVALUATION AND CALCULATION OF VARIABLES BY ASTRAZENECA

11.1 Calculation or derivation of efficacy variable(s) – Not applicable

11.2 Calculation or derivation of safety variable(s)

11.2.1 Other significant adverse events (OAE)

During the evaluation of the AE data, an AstraZeneca medically qualified expert will review the list of AEs that were not reported as SAEs and DAEs. Based on the expert's judgement, significant adverse events of particular clinical importance may, after consultation with the Global Patient Safety Physician, be considered OAEs and reported as such in the Clinical Study Report. A similar review of laboratory/vital signs/ECG data will be performed for identification of OAEs.

Examples of OAE are marked haematological and other laboratory abnormalities, and certain events that lead to intervention (other than those already classified as serious), dose reduction or significant additional treatment.

11.3 Calculation or derivation of patient reported outcome variables – Not applicable

11.4 Calculation or derivation of pharmacokinetic variables

The pharmacokinetic (PK) analyses will be performed at AstraZeneca R&D. The actual sampling times will be used in the PK calculations. PK parameters will be determined using standard non-compartmental methods. The following PK parameters will be determined:

Maximum plasma concentration (C_{max}), time to C_{max} (t_{max}), terminal elimination half-life ($t_{1/2}$), area under the plasma concentration-time curve from zero to infinity (AUC), area under the plasma concentration-time curve from zero to last measurable point (AUC_{0-t}), oral plasma clearance (CL/F).

11.5 Calculation or derivation of pharmacodynamic variable(s) – Not applicable

11.6 Calculation or derivation of pharmacogenetic variables – Not applicable

11.7 Calculation or derivation of health economic variables – Not applicable

12. STATISTICAL METHODS AND SAMPLE SIZE DETERMINATION BY ASTRAZENECA

12.1 Description of analysis sets

The classification of subjects into analysis sets will be made prior to the clean file meeting.

12.1.1 PK analysis set

All subjects who received at least one dose of investigational product and whose PK data are available without the protocol violations or deviations relating to inclusion/exclusion criteria, PK sampling and concomitant medications will be included in the PK analysis set.

12.1.2 Safety analysis set

All subjects who received at least one dose of investigational product will be included in the safety population.

12.2 Methods of statistical analyses

The statistical analyses will be performed by Statistics & Programming department, AstraZeneca K.K., Japan.

The coefficient of variation (CV) will be calculated as $100 \times \sqrt{\exp(s^2) - 1}$, where s is the standard deviation of the data on a log scale.

12.2.1 Demographic data

Age, sex, weight, height and BMI will be summarised using appropriate descriptive statistics.

12.2.2 Plasma concentration data

All plasma concentration of dapagliflozin will be listed by subject and summarised by dosing condition (with voglibose or without voglibose).

The plasma concentration of dapagliflozin at each time point will be summarised using the following descriptive statistics.

- Number of subjects

- Number of observations above LOQ
- Geometric mean
- CV
- Arithmetic mean
- SD
- Minimum
- Median
- Maximum

When calculating descriptive statistics, the plasma concentrations of dapagliflozin below LOQ will be substituted by LOQ/2.

The plots of individual and geometric mean plasma concentration of dapagliflozin over time for each dosing condition will be made.

12.2.3 PK parameter

All PK parameter will be listed by subject and summarised by the dosing condition.

All PK parameters, except for t_{\max} , will be summarised using the following descriptive statistics.

- Number of subjects
- Geometric mean
- CV
- Arithmetic mean
- SD
- Minimum
- Median
- Maximum

For t_{\max} , the following descriptive statistics will be presented.

- Number of subjects

- Minimum
- Median
- Maximum

The comparison between dosing condition for each PK parameters will be made based on complete case analysis. The pharmacokinetic variables AUC and C_{\max} will be log-transformed before analysis. To assess the effect of voglibose on the AUC and C_{\max} of dapagliflozin, they will be analysed using a mixed effect ANOVA model including the dosing condition (with voglibose or without voglibose) as fixed effect and patient as a random effect. Estimates and confidence intervals of the difference between the dosing conditions will first be constructed in the log scale. Then the estimates and confidence intervals of ratio of geometric means between the dosing conditions in the original scale will be obtained by taking anti-logarithms. The estimates and 2-sided 90% confidence intervals of the ratio of geometric means will be presented for:

- AUC (with voglibose) / AUC (without voglibose)
- C_{\max} (with voglibose) / C_{\max} (without voglibose)

It will be concluded that there is no pharmacokinetic drug-drug interaction if the confidence interval falls within 0.8 – 1.25 for AUC and C_{\max} of dapagliflozin. No adjustment for the multiplicity will be made.

The comparison between the dosing conditions for other PK parameters will be made in descriptive manner.

12.2.4 Safety data

All safety data will be listed for each individual patients and summarised across all patients by dosing conditions. The comparison between the dosing conditions for safety data will be made in descriptive manner.

All AEs during each PK sampling period and wash-out period will be listed and summarised by the System Organ Class and Preferred Terms assigned to the events using the Medical Dictionary for Regulatory Activities (MedDRA) vocabulary. Furthermore, listings of serious adverse events and adverse events that led to withdrawal will be made and the number of patients who had any adverse events, serious adverse events, adverse events that led to withdrawal, and adverse events with severe intensity will be summarised. If appropriate, adverse drug reactions will be summarised by the System Organ Class and Preferred Term assigned to the event using the MedDRA.

For the quantitative safety variables, the observed value and the changes from baseline at each time point will be summarised using the following descriptive statistics.

- Number of subjects

- Arithmetic mean
- SD
- Minimum
- Median
- Maximum

For all quantitative safety variables, the baseline will be the pre-dose value at Visit 2.

The number of patients in each category of qualitative safety variables at each time point will be summarised.

Laboratories values outside the reference range will be listed.

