3.1 Overall study design and flow chart

This is an open-label, multi-centre drug-drug interaction study to assess the effect of voglibose 0.2 mg tid on the pharmacokinetics (PK), safety and tolerability of dapagliflozin when a single oral dose of dapagliflozin 10 mg is administered to Japanese patients with type 2 diabetes mellitus (T2DM) treated with voglibose.

In this study 22 Japanese patients with T2DM will be assigned to treatment. The patients should be on stable treatment with voglibose at least 8 weeks before enrolment (one change in voglibose dose to 0.2 mg tid by 4 weeks before enrolment is allowed).

The study consists of two PK sampling periods: period I of a single dose of dapagliflozin with voglibose and period II of a single dose of dapagliflozin alone. The PK sampling periods will be separated by a wash-out period of 7(+7) days between the last blood sampling in period I and the dose of dapagliflozin in period II.

In period I, each patient will take a single oral dose of 10 mg dapagliflozin (Visit 2) together with voglibose and plasma samples will be collected through Visit 4 (up to 72 hours = 3 days after dose) for PK assessment. In period II, after the wash-out period, a single oral dose of 10 mg dapagliflozin will be administered without voglibose. Plasma samples will be collected through Visit 7 (up to 72 hours = 3 days after dose) for PK assessment.

The patients will take voglibose just before each meal (tid) until and including Study day 3 (Visit 4). The patients will stop taking voglibose on Study day 4 and no voglibose will be taken until after the last blood sampling for PK assessment on Study day 14 (Visit 7).

multiple ascending dose study (MB102025) was 1.5 times higher than healthy subjects) and the possible extension by interaction with voglibose, it is necessary to draw blood samples until 72 hours after dapagliflozin dosing. A wash-out period of 7 (+7) days between PK sampling periods is considered necessary in order for dapagliflozin and voglibose to be eliminated to remove carry-over effect. As study design, only single sequence fashion (combination followed by dapagliflozin mono-therapy) is adopted in terms of operational feasibility since it takes at least 4 weeks for voglibose to stabilize gastrointestinal condition and adverse events.

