6.4.7 ECG

6.4.7.1 Resting 12-lead ECG

A 12-lead ECG must be performed at Visit 2 (Day 0) and Visit 7.

A 12-lead ECG will be taken after the subject has been lying down resting. The ECG will be evaluated by the investigator and entered as 'Normal' or 'Abnormal' in the eCRF. If the ECG is evaluated as "Abnormal" the investigator should document the specific abnormality.

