6.7 Pharmacodynamics – Not applicable

6.8 Pharmacogenetics – Not applicable

6.9 Health economics – Not applicable

7. BIOLOGICAL SAMPLING PROCEDURES

7.1 Volume of blood

The samples will be processed by a central laboratory vender SRL Medisearch Inc.. Central laboratories will supply materials for blood sampling for the laboratory assessments and provide sample transportation.

The total volume of blood that will be drawn from each subject in this study is as follows:

Table 2 Volume of blood to be drawn from each subject

Assessment		Sample volume (mL)	No. of samples	Total volume (mL)
Safety	Clinical chemistry	7.0	7	49
	Haematology	2.0	7	14
	FPG	2.0	7	14
	HbA1c	2.0	7	14
	Hepatitis Screen Panel	10	1	10
Pharmacokinetic		3.0	30	90
Total				191

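### With Visit 2 as the only safety baseline, the period II change mixes the change after the second dapagliflozin dose with any shift since Visit 2

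*Protocol*

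**What the plan says.** Protocol Section 12.2.4 sets the layout of the safety tables: "All safety data will be listed for each individual patients and summarised across all patients by dosing conditions". For quantitative variables, "the observed value and the changes from baseline at each time point will be summarised". The reference value is the same throughout: "For all quantitative safety variables, the baseline will be the pre-dose value at Visit 2". No separate baseline for period II is defined elsewhere in the protocol. The contrast between conditions is informal: "The comparison between the dosing conditions for safety data will be made in descriptive manner".

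Section 3.1 gives the treatment status at each point. Patients enter on stable voglibose, and "In period I, each patient will take a single oral dose of 10 mg dapagliflozin (Visit 2) together with voglibose". After that, "The patients will stop taking voglibose on Study day 4 and no voglibose will be taken until after the last blood sampling". The second dapagliflozin dose follows at Visit 5 (Section 5.6), after a wash-out of 7 (+7) days. The sequence is the same for every patient: the combination first, dapagliflozin alone second.

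**The concern.** In period I the baseline is taken just before the dose whose effect is being described. Patients are on voglibose both then and afterwards, so the change describes what follows that dose.

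In period II the same Visit 2 value is used, although three things have happened since: voglibose has been stopped, a first dapagliflozin dose has been given, and a wash-out has passed. Section 5.6 also allows some non-antidiabetic drugs during the wash-out if medically needed. Two columns with the same label, change from baseline, thus describe different things.

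Section 2.2 makes the safety of dapagliflozin alone or with voglibose a secondary objective. Section 1.4 promises particular attention to blood pressure, electrolytes, renal function and liver function, and the baseline rule covers their quantitative measurements. A reader of the period II column could credit dapagliflozin with a change that was already present before the second dose.

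**Working it through.** The protocol states no figure on this point to reproduce. The check is timing plus algebra.

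**Age of the baseline.** Visit 2 is Day 0 (Section 6.4.7.1). Sampling runs 72 hours, to Day 3, and the wash-out is 7 (+7) days (Section 3.1).
- Earliest Visit 5: 3 + 7 = Day 10.
- Latest Visit 5: 3 + 14 = Day 17.
- Counting the wash-out from Study day 4 instead gives 4 + 7 = 11 and 4 + 14 = 18.

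The period II baseline is therefore about 10 to 18 days old at the second dose. In period I it is pre-dose on the day of dosing.

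**What each change contains.** Let Y2 and Y5 be the pre-dose values at Visits 2 and 5, and YI and YII the post-dose values in periods I and II. Let D be the mean change after a dapagliflozin dose, taken as equal in both periods for simplicity. Let W be the mean shift from Visit 2 to Visit 5, from all causes: stopping voglibose, elapsed time, carry-over from the first dose and wash-out medication.
- Period I, as planned: YI − Y2, mean D.
- Period II, as planned: YII − Y2 = (YII − Y5) + (Y5 − Y2), mean D + W.
- Period II from its own pre-dose value: YII − Y5, mean D.

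**Size over an assumed range.** The protocol gives no W. With D = 0.5, in units of the between-patient SD:

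| Assumed W | Period I change | Period II change from Visit 2 (D + W) | Period II change from Visit 5 (D) |
|---|---|---|---|
| 0 | 0.50 | 0.50 | 0.50 |
| 0.25 | 0.50 | 0.75 | 0.50 |
| 0.5 | 0.50 | 1.00 | 0.50 |
| 1.0 | 0.50 | 1.50 | 0.50 |

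A simulation of the four visit values gave the same means to two decimals. These rows show a range and do not estimate W.

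**The contrast between conditions.** For patients with both periods, (YII − Y2) − (YI − Y2) = YII − YI. The common baseline cancels, so the difference in mean changes equals the difference in mean observed values, here (D + W) − D = W. The change columns add nothing to this comparison beyond the observed values. With each period's own baseline the difference would be (YII − Y5) − (YI − Y2), with mean D − D = 0 here.

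**Are Visit 5 values available?** Section 7.1, Table 2 ("Volume of blood to be drawn from each subject") lists 7 samples each for clinical chemistry, haematology, FPG and HbA1c. That is consistent with one at each of Visits 1 to 7. Table 1 is not shown, so pre-dose timing at Visit 5 remains an assumption.

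**The case against.** The strongest case for the present rule is that one baseline before any study dapagliflozin is a coherent safety reference. It matches the physical-examination baseline in Section 6.4.6, shows cumulative change, and would reveal a lasting effect of the first dose that a Visit 5 baseline alone would hide. This stands, and it is a reason to keep the Visit 2 display alongside the new one.

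A reader might infer that the comparison between conditions is biased or spurious. The protocol does not support that. The baseline cancels, and what remains is a genuine contrast between dapagliflozin alone and dapagliflozin with voglibose. Being off voglibose is part of that contrast.

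A reader might also infer that the shift can never be isolated. If Visit 5 is sampled pre-dose, it can: observed values are tabulated at each time point and all data are listed by patient. Mean within-period change follows by subtraction when the same patients contribute; its SD, median and extremes need the patient listings. What the fixed sequence does prevent is dividing the shift between voglibose withdrawal and time, and a Visit 5 baseline would not cure that.

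Nor does the ECG share the problem. It is recorded as normal or abnormal, and "A 12-lead ECG must be performed at Visit 2 (Day 0) and Visit 7". It falls under the rule for qualitative variables, which counts patients per category at each time point, with no change from baseline.

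Finally, the shift may be small. Section 1.3 says that voglibose is not absorbed and acts on postprandial glucose, patients attend visits fasting (Section 5.1), and Section 1.4 expects no effect of two single dapagliflozin doses on glucose or lipid metabolism. This limits the likely size for many variables but leaves the composition of the period II change as it is.

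**Conclusion.** The point holds in a limited form. Section 12.2.4 fixes a rule under which the period II change equals the change after the second dose plus the whole Visit 2 to Visit 5 shift. That change cannot be read as the change after dapagliflozin alone. The excess is exactly W, whose size the protocol does not give.

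The shift should not be attributed to voglibose withdrawal alone, since time, carry-over and wash-out medication enter as well. There is also no basis in the protocol for claiming a material distortion in every safety variable.

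The consequence is modest. The safety comparison is secondary and descriptive, no test or decision depends on it, and the primary pharmacokinetic conclusion is untouched. The table above rests on assumed values of D and W and on equal D in both periods; the decomposition of the period II change does not depend on any of these.

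**What to change.** First confirm in the study plan (Table 1) that Visit 5 safety measurements are taken before the second dose. Then amend the baseline sentence in Section 12.2.4:
- Period I: change from the Visit 2 pre-dose value.
- Period II: change from the Visit 5 pre-dose value.
- Supplementary: change from Visit 2 at all later time points, including Visit 5 minus Visit 2 labelled as the wash-out change, so that any lasting effect of the first dose stays visible.

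The cost is a sentence or two of protocol text and one extra set of descriptive tables. Design and sample size do not change, and if the Visit 5 samples are pre-dose no further sampling is needed. If they are not, the period II change should carry a note that it includes the shift since Visit 2.
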